Dapagliflozin (Farxiga) is a potent and selective inhibitor of sodium glucose cotransporter 2 (SGLT2) and is approved by the FDA as an adjunct to diet and exercise to improve glycemic control in adults with T2DM. Dapagliflozin (Forxiga) is also approved in the EU as an adjunct to diet and exercise to improve glycaemic control in patients with T2DM for whom metformin use is considered inappropriate due to intolerance, and in combination with other glucose-lowering medicinal products when these, in combination with diet and exercise do not provide adequate glycemic control. Dapagliflozin is in a new class of compounds referred to as SGLT2 inhibitors. SGLT2 is localized to the renal proximal tubule where it reabsorbs most of the ~180 g of glucose normally filtered through the glomeruli each day. SGLT2 inhibition therefore leads to pharmacologically controlled glucosuria. Dapagliflozin is a highly selective and reversible inhibitor of SGLT2. A pharmacokinetic (PK) half-life of 12.5 hours, due to the C-aryl glucoside-derived chemical structure, allows for the oral administration of dapagliflozin once daily. Inhibition of glucose reabsorption leads to subsequent glycemic effects, including fasting plasma glucose (FPG) lowering and ultimately, effects on hemoglobin A1c (HbA1c). The HbA1c- and weight-lowering efficacy of dapagliflozin has been demonstrated in an extensive development program including more than 10,000 patients. The glycemic-lowering effect induced by SGLT2 inhibition is independent of the presence of insulin. Because of this insulin-independent mechanism of action, dapagliflozin has consistent effects on glycemic control in a wide spectrum of patients with T2DM, whether used as monotherapy at an early stage of disease or in combination with other oral anti-diabetes drugs (OADs) and/or insulin at a later stage, and may also be more likely to maintain its efficacy over time.

The combination of dapagliflozin and exenatide has not previously been studied. Because the 2 agents exert their glycemic and weight-lowering effects via different mechanisms, the simultaneous administration of the 2 compounds is expected to show additive effects on HbA1c and body weight.

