1.3.1 Ethical Safety Considerations

EQW has not previously been studied in combination with dapagliflozin. EQW may cause nausea due to delayed gastric emptying, an effect that tends to resolve over time, and dapagliflozin results in a mild osmotic diuresis. Both agents are associated with a modest systolic blood-pressure-lowering effect of approximately 2 to 4 mmHg. In addition, there have been reports of hypovolemia and prerenal azotemia with both agents, though the incidence of these events has been low. Since the combination of the 2 agents may potentially increase the risk of these events, investigators should be alert to signs or symptoms of these conditions. Blood pressure and renal function will be monitored at each study visit.

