2.2 Secondary objectives

Secondary Objective:	Outcome Measure:
To compare the effect of EQW + dapagliflozin to EQW + placebo and/or to dapagliflozin + placebo, on changes in glycemic control and anthropometric measures.	
 • Change in total body weight from baseline to Week 28. • Change in FPG from baseline to Week 28. • Change in 2-hour PPG after a standardized meal tolerance test at Week 28. • Proportion of patients achieving HbA1c <7.0% at Week 28. • Proportion of patients achieving weight loss $\geq 5.0\%$ at Week 28. • Change in FPG from baseline to Week 2. • Change in seated systolic BP from baseline to Week 28.

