3.9 Discontinuation of investigational product

Patients may be discontinued from the study medication in the following situations:

- Patient decision. The patient is at any time free to discontinue treatment, without prejudice to further treatment.
- Patient experiences an AE that, in the investigator's opinion, necessitates discontinuation from study medication.
- The investigator decides that the patient should discontinue study medication. If this decision is made because of a serious adverse event (SAE) or a clinically significant abnormal laboratory value, appropriate measures are to be taken. The Sponsor or its designee is to be alerted immediately. Refer to Section 6.4, Reporting of SAEs.
- Severe non-compliance with the study protocol.
- Calculated creatinine clearance <45 mL/min confirmed by repeat testing or a decrease in renal function that would preclude continued treatment with metformin according to local guidance.
- Loss of glucose control. If any patient experiences a loss of glucose control, in addition to study medication, the investigator should initiate rescue therapy and the patient may continue study participation. The

investigator should follow local prescribing information for the rescue therapy and may discuss appropriate rescue therapy with the AstraZeneca Medical Monitor if needed. Patients must first complete the Rescue visit procedures before receiving open-label rescue therapy. Rescued patients with central laboratory HbA1c values $>8.0\%$ despite a maximum tolerated dose of rescue therapy for 12 weeks will be discontinued from the study and referred for additional anti-hyperglycemic therapy (see Section 4.2).

- Patients with a central laboratory ALT and/or AST $>3x$ ULN will be scheduled for a follow-up visit within 3 days following the receipt of the result (see Appendix C, “Algorithm on Management of Sustained Elevated Liver Safety Abnormalities”). Patients should be discontinued from study medication if the initial and repeat laboratory tests meet any of the following criteria:
 - ALT and/or AST are $>3x$ ULN **and** TB $>2x$ ULN.
 - ALT and/or AST are $>5x$ ULN for ≥ 14 consecutive days, at any time after initial confirmatory results.
 - ALT and /or AST are $>8x$ ULN.

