The following will be performed during these visits:

- IVRS will be contacted to register the visit.
- AEs, potential CV event triggers (Section 6.8.1), and concomitant medications will be reviewed.
- A brief physical exam will be conducted (refer to Section 5.2.2).

- Vital signs (sitting systolic and diastolic BP and HR) will be assessed.
- Body weight will be measured.
- Blood samples will be collected **prior to administration of study medication** for the following assessments:
 - Chemistry and hematology
 - HbA1c (Visits 6, 7, 8, 9, 10, and 11 only)
 - Fasting plasma glucose will be collected at all treatment visits (need for rescue will be evaluated at Visits 7 to 11 only)
 - Serum creatinine (calculated creatinine clearance; Cockcroft-Gault formula)
 - Serum antibodies to exenatide (Visits 6, 7, 8, and 10 only)
 - Plasma exenatide and dapagliflozin (Visits 6, 7, 8, and 10 only).
- Urine will be collected for the following assessments:
 - Urinalysis
 - Urine glucose/creatinine ratio
 - Pregnancy test for all female patients, unless patient has had a hysterectomy.
- Patient diary will be reviewed.
- Visit 11 only: Patients will be instructed to perform 6-point SMBG on any 3 days in the week prior to Visit 12.
- Hypoglycemia episodes will be assessed.
- Diet and exercise counseling will be provided.
- Glucose meter and supplies will be provided.
- Study medication compliance will be reviewed.
- Study medication will be dispensed every 4 weeks during the treatment period: Visits 6 to 11. Study site personnel will monitor administration of injectable study medication (if the patient is due for an injection at the time of the visit).

- Instructions, reminders, and supplies (as appropriate) will be given to the patient (or designated caregiver) for proper transportation and storage of the study medication (to ensure temperature control, etc.).
- Rescue medication will be dispensed at Visits 7 to 11 if criteria for rescue medication are met (refer to [Table 3](#)).
- Used/unused study medication will be collected every 4 weeks (Visits 6 to 11).

4.2.2 End of Treatment Period Visit (Visit 12, Week 28) or Early Termination or Rescue during Treatment Period

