8.5.5.2 Clinical laboratory

Clinical laboratory results (chemistry, hematology, urinalysis, etc.) will be summarized using descriptive statistics for each visit by treatment group. Observed values at each visit and changes from baseline to each post-baseline visit will be presented. Changes from baseline in high/low/normal findings for clinical laboratory parameters for which normal ranges apply will be summarized by treatment group using shift tables. All laboratory data will be provided in patient data listings.

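### The only calculated renal-function measure on treatment, Cockcroft-Gault clearance, falls with body weight; if visit weight is used, by-arm summaries of its change will show a decline that is only weight loss

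*Protocol*

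**What the plan says.** Protocol 4.2.1 lists, among the blood assessments for Visits 4 to 11, "Serum creatinine (calculated creatinine clearance; Cockcroft-Gault formula"). The same item appears in 4.2.2, 4.3.1, 4.4.1 and 4.5, and Tables 1 and 2 carry it as a row. Section 4.2.1 also states "Body weight will be measured" at those visits. No section says whether current, baseline or some other weight enters the formula, and no estimate without weight is named.

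On the expected weight effect, section 1.1 says that giving the two drugs together "is expected to show additive effects on HbA1c and body weight". One of the secondary outcomes in 2.2 is "Proportion of patients achieving weight loss" of at least 5% at Week 28.

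On renal safety, section 1.3.1 notes a low incidence of hypovolemia and prerenal azotemia with both agents, allows that the combination may raise the risk, and responds: "Blood pressure and renal function will be monitored at each study visit". Section 3.9 lists among the situations for stopping study medication "Calculated creatinine clearance <45 mL/min confirmed by repeat testing"; criterion 15 in 3.2 excludes patients below 60 mL/min by Cockcroft-Gault.

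On reporting, section 5.2.1.2 puts creatinine and urea nitrogen in the chemistry panel. Section 8.5.5.2 says of clinical laboratory results: "Observed values at each visit and changes from baseline to each post-baseline visit will be presented", by treatment group.

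**The concern.** Body weight is a multiplier in Cockcroft-Gault clearance. In most trials this matters little, because weight moves alike in all arms. Here weight is an efficacy outcome that is expected to differ by randomized arm. A table of clearance change by arm would then mix the effect on weight with any effect on the kidney.

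Both push clearance down, and both would be largest in the combination arm if the expectation in 1.1 and the caution in 1.3.1 prove right. A reader of that table alone could not tell a renal effect from weight loss. At stake is the reading of one safety summary, on an organ the protocol says it is watching.

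**Working it through.** **Inputs from the protocol.** Cockcroft-Gault at each clinic visit where creatinine is scheduled; weight measured at the same visits; entry limit 60 mL/min; on-study limit 45 mL/min; 5% as the weight-loss size used in a secondary endpoint. The protocol states no expected weight loss in kilograms, no mean weight and no mean clearance, so it has no figure of its own to reproduce on this point.

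**Formula.** The protocol names Cockcroft-Gault without printing it. In standard form, clearance = (140 − age) × weight / (72 × serum creatinine in mg/dL), × 0.85 for women. For one patient, with the small and arm-independent effect of ageing left out:

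clearance(t) / clearance(0) = [weight(t) / weight(0)] × [creatinine(0) / creatinine(t)]

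**Step 1: unchanged creatinine, visit weight.** The second factor is 1, so a loss of x% in weight gives a fall of x% in clearance.

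| Weight loss | From 100 mL/min | From 60 mL/min |
|---|---|---|
| 2% | 98 | 58.8 |
| 3% | 97 | 58.2 |
| 5% | 95 | 57.0 |
| 10% | 90 | 54.0 |

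A 5% loss gives the same clearance as a creatinine rise of 1/0.95 − 1 = 5.3% at stable weight. With baseline weight, or with a measure that does not contain weight, every entry is zero change.

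**Step 2: between-arm artefact.** Assumptions: mean clearance 100 mL/min, mean weight 80 to 100 kg, 1 to 5 kg more loss in the combination arm than in a comparator, and percentage loss unrelated to baseline clearance. Artefact = 100 × (extra loss / mean weight).

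- Smallest: 100 × 1/100 = 1.0 mL/min
- Middle: 100 × 2/90 = 2.2 mL/min
- Largest: 100 × 5/80 = 6.25 mL/min

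**Step 3: does weight alone reach 45 mL/min?** From 60 mL/min the weight loss needed is 1 − 45/60 = 25%. A 5% loss covers 3 of the 15 mL/min between the two limits. It also lowers the creatinine rise needed to reach 45 from 60/45 − 1 = 33.3% to 57/45 − 1 = 26.7%. Both figures are for a patient who enters exactly at 60; anyone entering higher is further away.

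**Step 4: what is free of the artefact.** Serum creatinine and urea nitrogen contain no weight term. Tables 1 and 2 schedule the chemistry panel at the treatment-period and extension clinic visits, and 8.5.5.2 has it summarized by arm with change from baseline.

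**The case against.** The strongest reply is that the weight-free comparison is already planned. Creatinine and urea nitrogen will be tabulated by visit and arm, and azotemia can be read from them. This stands, and it limits the point to the clearance summary. A reader might infer that the whole renal safety comparison is biased against the combination; the protocol does not support that.

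Second, 8.5.5.2 does not name clearance as an analysis variable, safety is summarized descriptively, and 8.5.5 leaves details to the SAP. This also stands in part. No test on clearance is planned, and the SAP may already settle the weight convention. But the protocol itself fixes the formula as its one calculated renal measure, so proposing a weight-free one changes a stated method and does not just fill a blank.

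Third, the artefact needs visit weight, which the protocol does not specify. With baseline weight it vanishes. The point is therefore conditional.

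Fourth, Cockcroft-Gault is not arbitrary: section 1.2 ties the creatinine and clearance exclusions to the prescribing guidelines of the three drugs, and following the entry measure on study is coherent. That supports keeping it for those uses. It does not make it a good measure for comparing arms that lose different amounts of weight.

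Fifth, weight loss may lower creatinine generation, which would offset part of the artefact. The documents give no figure, so the sizes above are before any offset.

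**Conclusion.** The point holds in a limited form. If visit weight enters the formula, by-arm summaries of clearance change will contain a decline equal to the percentage weight loss, expected to be largest in the combination arm. Under the assumed ranges this is about 1 to 6 mL/min at a mean clearance of 100 mL/min. The proportionality is exact; the kilograms, the mean weight and the mean clearance are assumptions, and any offset from lower creatinine generation would reduce the figure.

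Two further readings are tempting and not supported. One is that weight loss will drive stops under the 45 mL/min criterion: it would take a 25% loss from the entry minimum to get there by weight alone, and a repeat test must confirm the value. The other is that azotemia is a risk specific to the combination: 1.3.1 attributes it to both agents, at low incidence, and says only that the combination may increase it.

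This is a modest improvement to a safety table at almost no cost. It does not undermine the trial's renal monitoring.

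**What to change.** This is a change to the analysis only. Base the between-arm summary of renal function on serum creatinine and on a weight-free eGFR derived from it. If change from baseline in Cockcroft-Gault clearance is tabulated, compute it with baseline weight, or show the baseline-weight and visit-weight versions side by side and label which is which.

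The cost is one derived variable and one table, built from samples already scheduled. The entry criterion and the discontinuation criterion, and the way each is applied, stay as they are.

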4.3 Extension Period 1 (24-week Extension period)

Patients will return for follow-up visits every 8 weeks during the long-term site-and patient-blinded Extension Period 1. Patients will monitor their fasting blood glucose levels at least once a week and will continue to enter the results into the patient diary. Diet and lifestyle modification will be reinforced at each visit during this period. Patients will be contacted approximately monthly between visits (as described in [Table 2](#)).

The need for initiation of rescue therapy will be assessed based on criteria in [Table 4](#). Patients must first complete the Rescue visit procedures before receiving open-label rescue therapy.

Table 4 **Criteria for initiation of rescue therapy during Extension Period 1**

Period	Central Laboratory HbA1c
From the day of Visit 13/Week 36 up to and including Visit 15/Week 52 and all unscheduled visits through the day prior to Visit 16/Week 65	HbA1c >8.0%

Note: Rescue upon receipt of HbA1c results. No repeat testing required for confirmation.

4.3.1 Extension Period 1 Visits (Visits 13 and 14, Weeks 36 and 44)

Prior to these visits, patients are to have fasted overnight (at least 8 hours). Patients should delay administering their morning dose of metformin and study medication on the morning of the study-site visit.

The following will be performed during these visits:

- IVRS will be contacted to register the visit.
- AEs, potential CV event triggers (Section 6.8.1), and concomitant medications will be reviewed.
- A brief physical exam will be conducted (refer to Section 5.2.2).
- Vital signs (sitting systolic and diastolic BP and HR) will be assessed.
- Body weight will be measured.
- Blood samples will be collected **prior to administration of study medication** for the following assessments:
 - Chemistry and hematology
 - HbA1c (need for rescue will be evaluated)
 - Fasting plasma glucose
 - Serum creatinine (calculated creatinine clearance; Cockcroft-Gault formula).
- Urine will be collected for the following assessments:
 - Urinalysis
 - Urine glucose/creatinine ratio

- Pregnancy test for all female patients, unless patient has had a hysterectomy.
- Patient diary will be reviewed.
- Visit 14 only: Patients will be instructed to complete 6-point SMBG profiles on any 3 days in the week prior to Visit 15.
- Hypo glycemia episodes will be assessed.
- Diet and exercise counseling will be provided.
- Glucose meter and supplies will be provided.
- Study medication compliance will be reviewed.
- Study medication will be dispensed every 8 weeks during Extension Period 1: Visits 13 and 14. Study site personnel will monitor administration of injectable study medication (if the patient is due for an injection at the time of the visit).
- Instructions, reminders, and supplies (as appropriate) will be given to the patient (or designated caregiver) for proper transportation and storage of the study medication (to ensure temperature control, etc.).
- Rescue medication will be dispensed at Visits 13 and 14 if criteria for rescue medication are met (refer to [Table 2](#)).
- Used/unused study medication will be collected.
- Between-visit telephone contacts will take place between Visits 13 to 16 for collection of safety information.

4.4 52-week Extension Period (Extension Period 2)

Patients will return for follow-up visits every 3 months (13 weeks) during the long-term site- and patient-blinded Extension Period 2. Patients will monitor their fasting blood glucose levels at least once a week and will continue to enter the results into the patient diary. Diet and lifestyle modification will be reinforced at each visit during this period. Patients will be contacted via telephone approximately monthly between visits (as described in [Table 2](#)).

The need for initiation of rescue therapy will be assessed based on criteria in [Table 5](#). Patients must first complete the Rescue Visit procedures before receiving open-label rescue therapy.

Table 5 **Criteria for initiation of rescue therapy during Extension Period 2**

Period	Central Laboratory HbA1c
From the day of Visit 16/Week 65 up to and including Visit 17/Week 78 and all unscheduled visits through the day prior to Visit 18/Week 91	HbA1c >7.5%
From the day of Visit 18/Week 91 up to and including the day before Visit 19/Week 104	HbA1c >7.0%

Note: Rescue upon receipt of HbA1c results. No repeat testing required for confirmation. Patients will discontinue study medication at the end of this treatment period (Visit 19, Week 104).

4.4.1 Extension Period 2 Visits (Visits 16, 17, and 18, Weeks 65, 78, and 91)

Prior to these visits, patients are to have fasted overnight (at least 8 hours). Patients should delay administering their morning dose of metformin and study medication on the morning of the study-site visit.

The following will be performed during these visits:

- IVRS will be contacted to register the visit.
- AEs, potential CV event triggers (Section 6.8.1), and concomitant medications will be reviewed.
- A brief physical exam will be conducted (refer to Section 5.2.2).
- Vital signs (sitting systolic and diastolic BP and HR) will be assessed.
- Body weight will be measured.
- Blood samples will be collected **prior to administration of study medication** for the following assessments:
 - Chemistry and hematology
 - HbA1c (need for rescue will be evaluated)
 - Fasting plasma glucose
 - Serum creatinine (calculated creatinine clearance; Cockcroft-Gault formula).
- Urine will be collected for the following assessments:

- Urinalysis
- Urine glucose/creatinine ratio
- Pregnancy test for all female patients, unless patient has had a hysterectomy.
- Patient diary will be reviewed.
- Visit 18 only: Patients will be instructed to complete 6-point SMBG profiles on any 3 days in the week prior to Visit 19.
- Hypo glycemia episodes will be assessed.
- Diet and exercise counseling will be provided.
- Glucose meter and supplies will be provided.
- Study medication compliance will be reviewed.
- Study medication will be dispensed every 13 weeks during Extension Period 2: Visits 16 to 18. Study site personnel will monitor administration of injectable study medication (if the patient is due for an injection at the time of the visit).
- Instructions, reminders, and supplies (as appropriate) will be given to the patient (or designated caregiver) for proper transportation and storage of the study medication (to ensure temperature control, etc.).
- Rescue medication will be dispensed at Visits 16 to 18 if criteria for rescue medication are met (refer to [Table 5](#)).
- Used/unused study medication will be collected.
- Between-visit telephone contacts will take place between Visits 16 to 19 for collection of safety information.

4.5 End of Extension Period 1 Visit (Visit 15, Week 52), End of Extension Period 2 Visit (Visit 19, Week 104), or Early Termination or Rescue Visit during Extension Period 1 or Extension Period 2

Prior to this visit, patients are to have fasted overnight (at least 8 hours), and to have abstained from strenuous exercise, alcohol, tobacco, and caffeine for 24 hours. Patients should delay administering the morning dose of metformin and study medication on the morning of the visit and bring oral antidiabetes medication and study medication to the study-site visit.

The following procedures will be conducted:

- IVRS will be contacted to register an End of Treatment Period Visit or Early Termination visit; the IVRS will not be contacted for a Rescue visit.
- AEs, potential CV event triggers (Section 6.8.1), and concomitant medications will be reviewed.
- A complete physical exam will be conducted (refer to Section 5.2.2).
- Vital signs (sitting systolic and diastolic BP and HR) will be assessed.
- 12-lead ECG will be performed.
- Body weight will be measured.
- BMI will be calculated.
- Waist circumference will be measured.
- Urine will be collected for the following assessments (to be collected right before time 0 of the meal tolerance test):
 - Urinalysis
 - Urine glucose/creatinine ratio.
- Meal tolerance test (MTT) will be performed (refer to Section 5.1.6).
